Statistical analysis: A portion of patients from Aim 1 will be randomized to one of two intervention arms (control then AFO, or AFO then control). We expect differences from a 3-month training to be larger than the immediate differences shown in Aim 1. A sample size of 30 subjects (15 per treatment arm) will provide 80% power to detect differences of 0.59 standard deviations between walking with and without an AFO, using a paired t-test for sample size estimation purposes only, and a significance level of 0.025 to adjust for multiple testing. This sample size will also allow us to detect an effect size of 1.2 for differences between the two groups at each time point. Assuming a 10% drop-out rate, we will randomize 17 per group, for a total of 34 subjects. For statistical analysis, a linear mixed modeling approach (or generalized linear mixed model, as appropriate) will be used. This approach will allow us to detect differences within and between groups, and adjust for confounding variables. The main comparison of interest will be changes in walking distances due to wearing the AFO. The use of the crossover design will allow us to investigate several questions of interest: 1) If walking distances improve after wearing the AFO for 3-months; 2) If walking distances worsen over the first 3 months for subjects not wearing the AFO in the first period; and 3) If the improvement in walking distances from wearing the AFO for three months is retained over the second 3 months (no AFO). To evaluate the relationship between improvements in walking performance, physical activity, and quality of life, and improvements in morphometric parameters, muscle oxygenation, and muscle strength and endurance, multiple correlations will be used. The level of significance will be set at p=0.05.

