Expected results/possible limitations: We hypothesize that an AFO intervention will increase walking performance, physical activity levels, and quality of life through improvements in the function of the muscles of the treated legs. If our hypothesis is correct, the AFO intervention is a new effective conservative intervention for patients with PAD. Because the premise is that the AFO will maintain overall torque and power while requiring a lower contribution from the leg muscles of patients, the patients will be able to walk further, placing less stress on their leg muscles, thereby allowing regeneration of structure and function of the muscles. Another possibility is that the patients experience an improvement in their walking performance, physical activity levels and quality of life but do not see improvements in muscular function of the legs. In this case, the

AFO would still be beneficial for patients to use. However, if none of the components of our hypothesis are correct, and neither the function and quality of life nor the muscle characteristics improve despite conscientious use of the AFO, then our study would direct us away from AFO-type treatments and towards other therapies and rehabilitation geared towards muscle health.

Specific Aim 3: Determine the feasibility of a three month AFO intervention

Approach: We will utilize Bowen and colleagues' standards for feasibility studies to measure the feasibility of using an AFO over three months in a random subset of 20 patients from Specific Aim 2. We will employ interviews and surveys throughout the three-month AFO intervention period to assess the following outcomes.

Outcomes

- 1) **Acceptability:** Interviews and a satisfaction survey will be implemented to assess satisfaction of using an AFO, intent to continue use, and perceived appropriateness measured. The research team will conduct interviews at 1.5 months, and three months. Interviews will last no longer than 30 minutes and will take place at the UNO Biomechanics Research Building. Satisfaction surveys for all participants will be completed during the final assessment in the Biomechanics Research Building.

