- 2) **Demand:** Actual use and perceived demand will be measured using an accelerometer and interviews. An additional accelerometer will be given to the patient at the baseline visit. Battery life on these accelerometers can span over 30 days, especially with a lower sampling frequency of 1 Hz. Each month a new accelerometer will be mailed to participants and the package will include a pre-paid mailer for subjects to return the previous accelerometer for downloading data and charging. Additionally, patients will be contacted randomly three times during the 3-month study period to further assess the actual use. Perceived demand will be assessed via interview at baseline and at three months.
- 3) **Implementation:** Degree of use, success/failure of use, and factors affecting the ease/difficulty of use will be measured using interviews to determine implementation. Interviews will take no longer than 30 minutes and will occur at 1.5 months and 3-month time points.
- 4) **Practicality:** Measurements of the positive/negative effects of the AFO and ability of participants to effectively use the AFO will be made to determine the practicality of the intervention. We will assess these factors via interviews at three months.

Analysis for Specific Aim 3, Outcomes 1-4: Data from interviews will be transcribed and analyzed by the research team in NVivo 10 (QSR International Pty Ltd., Victoria, AU). Researchers will independently code transcripts and meet to reach agreement on major data themes. Emerging themes will be identified using a constant comparison approach. This approach allows for the development of explanations through patterns but also allows the coder to harness theory and prior knowledge or research to answer research questions.

Statistical analysis: Descriptive statistics will be used to summarize results of survey data. We will use counts and percents for categorical data, and means and standard deviations for quantitative data. Associations between walking distance variables and acceptability, use, and practicality variables will be examined using t-tests for dichotomous variables and correlations for continuous variables.

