Expected results/possible limitations: We expect that an AFO intervention will be feasible to implement for three months in patients with PAD. If our hypothesis is correct, the study will establish the AFO as a new intervention that will likely be easily adopted by patients. It is also possible that the intervention does not prove feasible in one or more areas. If that happens, the study results will provide specific information on which aspects of the application of AFO treatment are not feasible. Those area(s) can then be further evaluated and potentially improved. Importantly, the results will inform the importance of these areas to feasibility of all interventions for the PAD patient group, not just the AFO intervention proposed in the current study.

Table 2: Project Timeline	1 st Year	2 nd Year	3 rd Year	4 th Year	5 th Year
Subject recruitment	XXXXXX	XXXXXX	XXXXXX	XXXXXX	XXX
Baseline assessment	XXXX	XXXXXX	XXXXXX	XXXXXX	
AFO and Control Intervention Arms	XXX	XXXXXX	XXXXXX	XXXXXX	XXX
Post AFO and Control assessments	XX	XXXXXX	XXXXXX	XXX	XXX
Data analysis		XXXXXX	XXXXXX	XXXXXX	XXXXXX
Abstract/manuscript development		XXX	XXXXXX	XXXXXX	XXXXXX
Grant writing				XXXXXX	XXXXXX

References

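### The Aim 3 satisfaction survey is given once, at the final on-site assessment, so early leavers have no survey score and completer-only percentages may overstate acceptability

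*Combined protocol and SAP*

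**What the plan says.** All references are to section 4 (Approach) of the combined protocol and SAP.

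- **Who is studied.** Specific Aim 3 measures feasibility "in a random subset of 20 patients from Specific Aim 2".
- **Which instruments measure acceptability.** Specific Aim 3, Outcomes, item 1: "Interviews and a satisfaction survey will be implemented to assess satisfaction of using an AFO, intent to continue use, and perceived appropriateness measured". The two instruments are named jointly for all three items.
- **When and where.** For interviews: "The research team will conduct interviews at 1.5 months, and three months", and they "will take place at the UNO Biomechanics Research Building". For the survey: "Satisfaction surveys for all participants will be completed during the final assessment in the Biomechanics Research Building".
- **How results are summarised.** Interview data are transcribed, coded and reduced to themes. For survey data, Specific Aim 3, Statistical analysis, says: "We will use counts and percents for categorical data, and means and standard deviations for quantitative data". It gives no denominator and no rule for a missing survey.
- **Expected loss.** The only drop-out figure is in Specific Aim 2, Statistical analysis: "Assuming a 10% drop-out rate, we will randomize 17 per group, for a total of 34 subjects".
- **Other contact in the AFO period.** Item 2 (Demand) plans monthly accelerometer mailings and three contacts at random times. The stated purpose of both is to measure actual use, not satisfaction.
- **Intended conclusion.** If the feasibility hypothesis is correct, "the study will establish the AFO as a new intervention that will likely be easily adopted by patients". The same paragraph also allows for a finding of infeasibility in one or more areas.

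**The concern.** For most outcomes a missing value is simply missing. For the acceptability of a device worn daily, leaving during the wearing period may itself be a sign of the outcome. The survey is the only acceptability measure that the plan says it will turn into percentages, and it exists only for patients who come back for the last visit. Nothing else in the documents obtains a survey score from someone who stops and leaves, and nothing says how that patient counts. The default is then a percentage of returned surveys.

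At stake is the descriptive acceptability figure that would support a statement about easy adoption. The background section on adherence faults an earlier device study for not learning from patients why they did not wear the device. A single end-of-study survey risks missing the patients best placed to say so. The planned tests of association between walking distance and acceptability would lose the same patients wherever they use survey scores.

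**Working it through.** **Inputs.** From the documents: 20 patients in Aim 3; 10% drop-out, 30 evaluable and 34 randomised in Aim 2. Assumed: the share satisfied, because no rate is given, and the share of the loss that falls in the AFO period.

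**1. The plan's own figure.** 30 / 0.90 = 33.3, rounded up to 34; per group, 15 / 0.90 = 16.7, rounded up to 17. The stated 34 reproduces. The 4 extra patients (4/34 = 11.8%) come from rounding up and are not a second drop-out assumption.

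**2. General form.** Let N patients be issued an AFO and m have no survey. Let p be the share satisfied among the N − m surveyed and q the share satisfied among the m not surveyed. Then

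completer percentage − percentage among all issued = (m/N) × (p − q).

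The completer figure is too high only if p > q. The extremes are p × m/N too high (q = 0) and (1 − p) × m/N too low (q = 1).

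**3. Aim 3 subset, 10% loss applied in full.** m = 0.10 × 20 = 2, so 18 are surveyed.

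| Satisfied among surveyed | Completer figure | Both leavers not satisfied | Both leavers satisfied |
|---|---|---|---|
| 14/18 | 77.8% | 14/20 = 70.0% | 16/20 = 80.0% |
| 16/18 | 88.9% | 16/20 = 80.0% | 18/20 = 90.0% |
| 18/18 | 100% | 18/20 = 90.0% | 20/20 = 100% |

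The overstatement is 7.8, 8.9 and 10.0 points in turn, and 10 points is the ceiling. In the first row the completer figure could instead be 2.2 points too low.

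**4. Only half the loss in the AFO period (assumed).** m = 1. At an assumed 80% satisfied, the overstatement is at most 0.80 × 1/20 = 0.04, that is 80% against 76%.

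**5. If the survey goes to all 34 Aim 2 patients.** 10% is about 3. Then 25/31 = 80.6% lies against a range from 25/34 = 73.5% to 28/34 = 82.4%, and the ceiling is 3/34 = 8.8 points.

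**6. Scale.** At 80% satisfied and 18 surveyed, the standard error is √(0.80 × 0.20 / 18) = 9.4 points. The worst case at that rate, 0.80 × 2/20 = 8.0 points, is about 0.85 of a standard error. With an assumed 20% or 30% missing out of 20, the ceiling rises to 20 or 30 points.

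**The case against.** The strongest reply is that this is a small reporting gap, and that several stronger readings of it fail. Much of that stands.

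- **A reader might infer that satisfaction is collected only at the end, and intent to continue only at interview.** The Acceptability item does not say so. It assigns both to interviews and survey together, so a patient who leaves after 1.5 months can have interview data on both. Those data are qualitative, however, and the plan does not carry them into the survey percentages.
- **A reader might infer that every Aim 3 result becomes a percentage.** The statistical paragraph says this of survey data only. Success or failure of use is assessed by interview, so the plan defines no success rate that could be biased in this way.
- **A reader might infer that the bias must run towards feasibility.** Step 2 shows that this needs leavers to be less satisfied than completers, and the plan never states a completers-only denominator. Overstatement is likely but not certain.
- **A reader might count the full 10% as AFO failures.** The figure is an Aim 2 allowance for the whole crossover. Some patients may leave before receiving the AFO, and others in a later control period, so loss during AFO wear may be lower.
- **Feasibility does not rest on the survey alone.** Accelerometers and random contacts can show non-use before the last visit, the adoption statement is conditional, and no threshold is set.
- **Scoring each leaver as a refusal would assign an answer the patient never gave.** It also would not restore that patient's missing walking distance for the association tests.

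None of these points supplies a survey score for a patient who leaves early, or a denominator for the percentages.

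**Conclusion.** The gap is real and limited to the survey. As written, a patient who stops the AFO and leaves has no survey score, and a percentage based on completers may overstate acceptability. If the Aim 2 drop-out applied fully to the 20 patients, the overstatement would be at most 10 points, and about 4 points at an assumed 80% satisfied if half the loss falls in the AFO period. The completer figure could also be about 2 points too low. These sizes rest on assumed satisfaction rates and on a drop-out figure borrowed from Aim 2. The documents do not support a claim of certain one-way bias, or of bias across all feasibility measures.

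Two ambiguities affect the size. The survey sentence does not say whether it covers the 20 Aim 3 patients or everyone in Aim 2. It also does not say whether the final assessment closes the AFO period or the whole crossover. On the second reading, patients assigned AFO first who finish wearing it but leave during the control period would also lack a score.

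Priority is low: Aim 3 is descriptive, has no decision threshold, and about one or two patients of the 20 are affected at the assumed loss.

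**What to change.** 1. Give the existing satisfaction survey at the end of each patient's AFO period. When a patient stops the AFO or leaves during that period, give it by phone or mail and record the reason. State whether the survey covers the Aim 3 subset or all Aim 2 patients.
2. Report survey percentages over all Aim 3 patients issued an AFO, with those not surveyed shown as their own category. Give the numbers issued, surveyed and lost, with reasons, and put the completers-only percentage beside them. Patients who leave before receiving an AFO are not in the denominator.
3. Show the result with all unsurveyed leavers counted as not satisfied, and as not intending to continue, as a sensitivity bound only. It should not be entered as an imputed answer.

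The cost is a few sentences in the Aim 3 analysis and one short phone or mailed survey for a few patients: about 2 of 20 at the assumed loss, or 3 to 4 if all 34 are surveyed. The nurse-coordinator contact and the pre-paid mailings already planned can carry it. The downside is that the published percentage may look less favourable.

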AFO and Control Intervention: Patients will be asked to wear an AFO each day for three months. Subjects will have an off-the-shelf AFO (Figure 2) chosen initially based on shoe size and adjusted or exchanged for a different size during the initial evaluation after entering the study. The patients will be asked to wear the AFO at all times except when they are in bed or showering/bathing. The instructions given to the patients about walking will be the same as typically provided by clinicians, which is to walk 30 minutes per day, most days/week. We have chosen this specific AFO device because it is already available for use in a clinical environment, is composed of a carbon-composite material that will capture and return energy during the gait cycle, and has successfully contributed to propulsion during walking in other clinical populations^{26, 28}. Patients will be able to contact the nurse coordinator at any time if they need the AFO adjusted or have questions about what should happen during the intervention. Subjects in the control arm will be asked to continue the same lifestyle for three months. The intervention arm order will be randomized (see Statistical Analysis)

Outcomes: All outcomes will be assessed at baseline and following each arm (control and AFO).

- 1) Initial and absolute walking distances, 2) Lower extremity torque and power, 3) Muscle activity, and 4) Energy cost will all be measured as described for Specific Aim 1.
- 5) **Physical Activity:** Participants will wear the Actigraph (Actigraph GT3X, Actigraph, FL, USA) accelerometer on their hip for seven days (the whole day except when sleeping) prior to starting the AFO intervention to measure baseline activity level. The accelerometer will be mailed back to researchers in a pre-paid envelope. Two weeks prior to the post-intervention visit to the laboratory, an accelerometer will be mailed to participants to wear the final seven days before the visit. Average steps/day, maximum cadence, and average peak activity index will be calculated.

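### Aim 3 relates AFO use to walking distance without adjusting for starting distance, so a use score that carries any movement signal would partly reflect how well the patient already walked

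*Combined protocol and SAP*

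**What the plan says.** All references are to section 4, Approach.

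- **Source of the use data (Specific Aim 3, Outcomes, 2 Demand).** "Actual use and perceived demand will be measured using an accelerometer and interviews". The device is a second one: "An additional accelerometer will be given to the patient at the baseline visit". It is exchanged monthly by post. Self-report is added: "patients will be contacted randomly three times during the 3-month study period to further assess the actual use".
- **A further source (Outcomes, 3 Implementation).** "Degree of use, success/failure of use, and factors affecting the ease/difficulty of use will be measured using interviews to determine implementation", at 1.5 and 3 months.
- **What patients are asked to do (Specific Aim 2, AFO and Control Intervention).** "The patients will be asked to wear the AFO at all times except when they are in bed or showering/bathing". Prescribed use is therefore wear time.
- **Analysis (Specific Aim 3, Statistical analysis).** "Associations between walking distance variables and acceptability, use, and practicality variables will be examined using t-tests for dichotomous variables and correlations for continuous variables". No covariate is named.

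The plan does not state where the additional monitor is attached, the unit of use (hours, days or counts), how sitting still in the AFO is told from not wearing it, or how the sources are combined. The only accelerometer summaries defined anywhere are the step, cadence and activity measures from the hip monitor in Aim 2.

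**The concern.** Use is prescribed as hours worn, but an accelerometer senses motion. Without a rule that turns motion into wear, a use score can rise because the patient moves more and not because the AFO is worn longer. A body-worn monitor would also count walking without the AFO. A monitor on the AFO, read without a rule for stillness, would miss seated wear, which matters in patients whom the Significance section describes as sedentary.

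Patients who walk further on the treadmill at the start are likely to walk further on it later, and may also move more each day. A raw correlation between use and later distance then has a common cause: starting ability. It could look like a benefit of using the AFO more when there is none.

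What is at stake is the reading of adherence. The Significance section blames low wear time for part of a poor result in an earlier off-loading study, and the Aim 2 discussion would interpret a null result in the light of conscientious use. Both need a use measure that is not a proxy for walking ability.

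**Working it through.** **No figure to reproduce.** The documents give no power, effect size or target correlation for this association, so the check is an illustration under stated assumptions.

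**Inputs from the documents**
- n = 20, a random subset of Aim 2 patients (Specific Aim 3, Approach).
- Two-sided 0.05. Aim 3 states no level, so this is borrowed from Aim 2.
- Distance is a progressive treadmill distance (Aim 1, Outcome 1), measured at baseline and after each arm (Aim 2, Outcomes).

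**Assumptions (not in the documents)**
- Correlation between daily activity rate and starting distance, ρ: 0.3, 0.5, 0.7.
- Correlation between starting and post-AFO distance, r: 0.6, 0.75, 0.9.
- Between-patient CV of activity rate 0.5; CV of wear time 0, 0.3, 0.5.
- Distance, activity and wear are lognormal (SD of log distance 0.4).
- Wear time is unrelated to distance and has no effect on it.
- Use score = wear time × activity rate, so it carries a movement signal.

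**Threshold.** Critical |r| = t/√(df + t²). Unadjusted, df = 18: 2.101/√(18 + 4.414) = 0.444. With one covariate, df = 17: 2.110/√(17 + 4.451) = 0.456.

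**Expected size of the spurious correlation (log scale).** ρ × r × s_a/√(s_a² + s_w²), where s_a and s_w are the log SDs of activity and wear.
- Weakest setting: 0.3 × 0.6 × 0.707 = 0.13.
- Strongest setting: 0.7 × 0.9 × 1 = 0.63.

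**Simulated false-positive rate of the raw correlation (20,000 runs per cell, distances in metres)**

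| ρ | r | wear CV 0 | wear CV 0.3 | wear CV 0.5 |
|---|---|---|---|---|
| 0.3 | 0.6 | 12% | 11% | 9% |
| 0.3 | 0.75 | 16% | 13% | 11% |
| 0.3 | 0.9 | 21% | 17% | 13% |
| 0.5 | 0.6 | 24% | 19% | 15% |
| 0.5 | 0.75 | 34% | 26% | 20% |
| 0.5 | 0.9 | 49% | 36% | 26% |
| 0.7 | 0.6 | 43% | 32% | 23% |
| 0.7 | 0.75 | 64% | 47% | 33% |
| 0.7 | 0.9 | 83% | 64% | 46% |

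The range is roughly 9% to 80%. At ρ = 0 it is 5%. If use is true wear time, it is about 5% at every ρ.

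**Same data with starting distance as covariate.** The rate is 5% with distances on the log scale and 6% to 9% in metres, where a linear adjustment does not fit skewed distances exactly.

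**Change score without the covariate.** The rate is 7% to 31% in metres. Change is negatively related to starting distance when r is below 1, so a spurious association remains, now of opposite sign. Adding starting distance as covariate makes change and post-AFO distance give the same coefficient for use.

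**Limit of the adjustment.** Suppose instead that both treadmill tests are noisy readings of one underlying ability to which activity is tied. The raw rate is then 15% to 93% (wear CV 0 or 0.5), and the adjusted rate is 7% to 57%. Adjustment helps in every cell but does not fully repair a movement-based score, so the definition of use also matters.

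**The case against.** The case against is substantial.

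- **Use does not come from the accelerometer alone.** Interviews and random contacts also assess it, and the analysis does not say which use variable is tested. This stands: the bias applies to the accelerometer score, or to a composite that contains it.
- **The plan nowhere scores use as steps or counts.** Those summaries belong to the hip monitor in Aim 2. A monitor on the AFO, with a suitable stillness rule, can give wear periods. This stands too. A reader might infer that the association is bound to be false; the documents support only a conditional statement.
- **Silence on change scores is not exclusion.** Walking distance variables could include change. That is right, but change alone does not remove the problem, as the working shows.
- **The rates are assumed.** The outcome is a treadmill distance, not daily walking, and the documents give no correlation between the two. That is why a range is shown. A reader might quote only the case of identical wear with activity tied directly to the tested distance: 25%, 59% and 93% at ρ = 0.3, 0.5 and 0.7. Identical wear removes the very variation that Aim 3 sets out to measure, so this should not be the headline.
- **The 1 Hz sampling rate.** A reader might argue that it is too slow to count steps. The plan does not say that this device counts steps, so the point has no bearing.
- **Aim 3 is a feasibility aim**, mostly interviews and description, with no hypothesis test powered for this association. This limits the importance of the point but does not remove it.

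**Conclusion.** The point holds in a limited form. Aim 3 plans unadjusted tests of use against walking distance, with one use source undefined as to placement, unit and wear rule. If that source carries a movement signal, starting walking ability confounds the association. The size is roughly 9% to 80% false positives instead of 5%, for 20 patients and assumed activity–distance correlations of 0.3 to 0.7. It rests on assumed values for the variation in wear and for the link between starting and later distance. With no activity–distance correlation, or with use derived as true wear hours, the excess disappears.

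The missing placement and wear rule alone would be a gap in detail. What makes this worth acting on is that the stated analysis leaves out a covariate the trial already collects. A reader might infer that the trial's efficacy results are at risk. They are not: the Aim 1 with-and-without comparison and the Aim 2 crossover comparison do not use this variable.

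**What to change.** **Analysis (main change).** Replace the raw t-tests and correlations between use and walking distance with a regression of post-AFO distance, or its change, on use, with distance at the start of the AFO period as covariate. For patients who have the AFO first, that is the baseline test; for those who start with control, it is the test at the end of the control period. Both are already planned. Consider log distance if distances are skewed. The cost is one degree of freedom and a sentence in the plan.

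**Measurement.** State that the additional monitor is fixed to the AFO. Derive use as AFO wear hours per day over the whole three months, with a pre-stated non-wear rule that bridges periods of sitting. Keep step and activity counts out of the use variable. Report interview and contact data on wear separately. The cost is a means of attachment and a processing rule, with monitors already planned; the non-wear rule needs a short check that it separates seated wear from an AFO set aside.

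A tempting alternative is the share of hip-recorded moving minutes in which the AFO monitor also moves. It should not be the main measure: it leaves out seated wear and exists only for the seven days when the hip monitor is worn.

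### A question about negative effects of the AFO is specified only at three months and only in the 20-patient Aim 3 subset; none is specified for the other 14 randomised patients or for those who leave early

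*Combined protocol and SAP*

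**What the plan says.** All places are in the combined protocol and SAP, section 4 (Approach).

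- **Exposure.** Specific Aim 2, AFO and Control Intervention: "The patients will be asked to wear the AFO at all times except when they are in bed or showering/bathing". The AFO period lasts three months.
- **Number randomised.** Specific Aim 2, Statistical analysis: "Assuming a 10% drop-out rate, we will randomize 17 per group, for a total of 34 subjects".
- **Who is in Aim 3.** Specific Aim 3, Approach: feasibility is studied "in a random subset of 20 patients from Specific Aim 2".
- **Where negative effects are named.** Specific Aim 3, outcome 4 (Practicality): "Measurements of the positive/negative effects of the AFO and ability of participants to effectively use the AFO will be made". On timing and method, the same item says "We will assess these factors via interviews at three months".
- **Other contacts during or after AFO wear.**
  - The Implementation interviews at 1.5 and three months have this content: "Degree of use, success/failure of use, and factors affecting the ease/difficulty of use will be measured using interviews to determine implementation".
  - The Acceptability interviews and survey cover satisfaction, intention to go on using the device and perceived appropriateness. The survey is given to all participants at the final assessment.
  - Three randomly timed contacts check actual use.
  - Aim 2 patients may call the nurse coordinator at any time about adjustment or with questions.

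The visible text has no definition of an adverse event, no schedule for asking about harm, and no exit interview.

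**The concern.** The device is to be worn for nearly all waking hours by patients with an ankle/brachial index below 0.90. The entry criteria call for a stable diabetes regimen, so patients with diabetes can enter; rest pain and tissue loss are excluded at entry. A plan of this kind should ask everyone exposed, in the same way, whether the device caused trouble. Here the specified question has one time point, the end of the period, and covers only part of the exposed group.

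Two groups fall outside it: patients not drawn into the subset, and subset patients who leave before three months. If some of the second group leave because of the device, they are the ones whose experience matters most for practicality.

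The plan's own purpose is at stake. The Significance section counts negative effects as part of practicality. It also faults the literature on another worn device for lacking the patients' own reasons for poor adherence. The closing text of Aim 3 looks to conclude that patients would readily adopt the AFO, or else to identify which aspects are not feasible. Aim 3 also relates practicality variables to walking distance. All of this would draw on negative-effects data mainly from subset patients still in the study at three months.

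**Working it through.** **1. Reproduce the plan's denominator.** Inputs are from Specific Aim 2, Statistical analysis: "A sample size of 30 subjects (15 per treatment arm) will provide 80% power to detect differences of 0.59 standard deviations", at "a significance level of 0.025 to adjust for multiple testing", with 10% drop-out.

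- Power of a paired t-test with effect 0.59 SD, n = 30 and two-sided alpha 0.025 is 80.2%, against 80% stated. The plan does not state sidedness; two-sided reproduces its figure.
- Inflation for drop-out: 30 / 0.9 = 33.3, rounded up to 34; per sequence 15 / 0.9 = 16.7, rounded up to 17. Both match the plan.

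**2. Who has a specified negative-effects question.** The subset of 20 is from Specific Aim 3, Approach.

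- Of those randomised: 34 − 20 = 14 have none, and 14 / 34 = 41%.
- Of the 30 expected completers, if all 20 in the subset complete: 30 − 20 = 10, and 10 / 30 = 33%.
- If the subset also loses 10%: 20 × 0.9 = 18 reach the interview, leaving 30 − 18 = 12 completers not asked.

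**3. What the smaller number costs in information (illustration).** The like-for-like comparison applies drop-out to both sides: about 18 asked under the plan, and about 30 if every completer were asked at the end-of-AFO visit. Drop-out is taken here as unrelated to harm.

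If no event is seen, the one-sided 95% upper limit on the rate is 1 − 0.05^(1/n):

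- n = 18: 1 − 0.05^(1/18) = 15.3%
- n = 30: 1 − 0.05^(1/30) = 9.5%

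The chance of seeing at least one case at true rate p is 1 − (1 − p)^n. The documents give no harm rate, so p is an assumption, shown over a range:

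| Assumed rate | n = 18 | n = 30 |
|---|---|---|
| 2% | 30.5% | 45.5% |
| 5% | 60.3% | 78.5% |
| 10% | 85.0% | 95.8% |

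**4. Early leavers.** At 10% drop-out about 2 of the 20 subset patients would have no three-month interview. If they left because of the device, the practicality data would contain none of those events. The table does not show this loss, because it treats drop-out as unrelated to harm.

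**5. Could another contact carry the question?** Set beside Practicality, each other contact has different stated content: use and ease of use, satisfaction and intention, actual use, or calls that the patient must start. None names negative effects.

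**The case against.** The strongest reply is that the plan has several ways for a problem to surface, and that silence in the text does not prove that nobody asks. Much of this stands, and it rules out four stronger readings that a reader might infer.

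- **That the other 14 are never asked about harm.** The documents do not establish this. The satisfaction survey is for all participants, which may mean all of Aim 2 or only the 20, and its questions are not reproduced. What can be said is that its listed content does not include negative effects.
- **That anyone who stops the AFO early is missed.** Stopping the device is not leaving the study. Outcomes are assessed after each arm, and nothing bars a subset patient who has stopped wearing the AFO from the three-month interview. The gap is established only for patients who leave the study.
- **That problems cannot surface before three months.** The nurse coordinator can be called at any time. In the subset, the 1.5-month interview on whether use succeeded or failed is a natural opening, and accelerometers and random contacts would show early abandonment as non-use. Walking distance and quality of life are also measured in all Aim 2 patients after each arm, though a decline there is not attributed to the device.
- **That the trial has no arrangements for reporting harm.** The consent pages were removed, so instructions given to patients there cannot be checked.

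Two further points are fair. The interviews are analysed for themes and are not designed to estimate a rate, so the figures above only illustrate the information lost. Also, 34 is the largest number that could be exposed, because a patient in the control-first sequence may leave before wearing the AFO.

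The reply does not supply a specified question on negative effects outside the three-month subset interview. A volunteered complaint, or a remark made while discussing use, is not a uniformly collected outcome with a known denominator.

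**Conclusion.** The concern holds in limited form. The visible plan specifies a negative-effects question once, at three months, in 20 of 34 randomised patients. It specifies none for the other 14 (41% of those randomised; 10 of the 30 expected completers if the whole subset completes), and none for patients who leave the study before three months. The practicality conclusion would therefore rest mainly on subset patients still in the study at three months and could understate harm.

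Under the plan's 10% drop-out, about 18 rather than 30 patients would be asked. The zero-event upper limit is then 15.3% rather than 9.5%. At an assumed 5% harm rate, the chance of seeing at least one case is 60% rather than 79%. These figures assume that drop-out falls evenly on the subset and is unrelated to harm; if device problems cause drop-out, the understatement is larger. This is a correctable gap in measurement and does not affect the walking-distance analysis.

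**What to change.** Revise outcome 4 (Practicality) in Specific Aim 3 so that a short, uniform negative-effects checklist, including the reason for any stopping, is:

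- given to all Aim 2 patients at the existing end-of-AFO visit;
- added to the existing 1.5-month interviews and random use contacts;
- asked by telephone when a patient stops the AFO or leaves the study.

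In the Aim 3 statistical analysis, state that the proportion with any negative effect will be reported among all patients who received the AFO, counting early stoppers. This denominator also deals with control-first patients who leave before wearing the device. Keep the in-depth qualitative interview in the subset of 20, and state whether the satisfaction survey goes to the subset or to all of Aim 2.

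The cost is a little visit and call time, mostly at contacts that already exist, with no extra patients. The tolerability figure may look less favourable. How a reported problem is handled clinically is for the investigators to set.
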